6 STUDY INTERVENTION DISCONTINUATION AND SUBJECT DISCONTINUATION/WITHDRAWAL

6.1 DISCONTINUATION OF STUDY INTERVENTION

Not applicable

6.2 SUBJECT DISCONTINUATION/WITHDRAWAL FROM THE STUDY

Not applicable

6.3 LOST TO FOLLOW-UP

Not applicable

7 STUDY ASSESSMENTS AND PROCEDURES

7.1 STUDY ASSESSMENTS

AWEI study outcomes are tracked and recorded by AMPLIFI recruiters who are blind to the AWEI random assignment. No other assessments are conducted.

To allow for the AWEI interventions to be delivered, we allow 15 days from the time from when the recruitment letter was sent to when the AMPLIFY recruitment call occurred.

To further ensure that AMPLIFY recruiters remain blind to study assessment, AWEI participants, including those in the no AWEI control arm, are “released” to the recruiters in a random fashion over the 15 days AWEI period starting at day 8. For the AWEI RE arm, survivors are released after the RE call is completed or the RE completed all 7 attempts to deliver the intervention.

Survivors reached by AMPLIFY recruiters are given more information about the study and given the option to be screened for participation to verify additional inclusion (e.g., completed primary treatment) and exclusion criteria (e.g., conditions that would make unsupervised exercise unsafe). If they screen eligible and are interested in joining AMPLIFY, they would undergo the informed consent process and enroll in AMPLIFY.

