5.1.2 DOSING AND ADMINISTRATION

In the AWEI-Research Educator (RE) arm, one of four REs attempted to contact survivors by phone starting 5 days after the letter was sent (7 attempts over 10 days) and deliver the content of the intervention following a script. Each RE was trained on the

script of one of the AWEI-RE combinations differing by Information Emphasis and Perspective to avoid contamination across AWEI groups. If the survivor did not receive the recruitment letter, the RE would give more information about the purpose of the call and offer to resend the letter.

In the AWEI-Brochure arm, one of 4 brochures according to AWEI combination was sent 4 days after the recruitment letter was sent. The same content was delivered in the AWEI-RE and AWEI-Brochure arms.

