8.2 SAMPLE SIZE DETERMINATION

Hypothesis 1: AWEI (any combination) will have a significantly higher recruitment yield than the basic AMPLIFY recruitment strategy (no AWEI control group).

With a minimum of 1,600 in the AWEI intervention group, and 400 in the no AWEI control group, a two-sided chi-square test (for unequal sample sizes), and a 5% significance level, we will have > 95% power to detect a statistically significant difference in recruitment yield of 10% vs. 20%.

Hypothesis 2 - Delivery channel: AWEI-Research Educator will have a significantly higher recruitment yield than AWEI-brochure

Hypothesis 3 - Information emphasis: Education content with study-specific emphasis will have a significantly higher recruitment yield than with research general emphasis

Hypothesis 4 - Perspective: Education content delivered from the survivor perspective will have a significantly higher recruitment yield than education content delivered from the researcher perspective.

For these hypotheses, with a minimum of 800 per group, a two-sided chi-square test, and a 5% significance level, we will have > 95% power to detect a statistically significant difference in recruitment yield of 10% vs. 20%.

Hypothesis 5: AWEI-Research Educator with study-specific emphasis and cancer survivor perspective (combination #3, Table 1) will be the most efficacious.

The same sample size calculation applies to the comparison of any two combinations. With a minimum of 200 per group, a two-sided chi-square test, and a 5% significance level, we will have 80% power to detect a statistically significant difference in recruitment yield of 10% vs. 20%.

Calculations were performed using nQuery Advisor + nTerim, version 3.0.

Thus, the trial is fully powered with a sample of 2,000 survivors, 200 in each AWEI combination, and 400 in the no AWEI arm. However, we will randomize all survivors identified from the cancer registries. If these are less than 2000, we will expand to other

cancer registries (estimated numbers from these registries exceed 2000 survivors). If these are more than 2000, we will randomize all.

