8.3 STATISTICAL ANALYSES

8.3.1 GENERAL APPROACH

An intent-to-treat approach is used for statistical analyses. Descriptive statistics, including frequencies and proportions, are obtained for study variables. Differences between the group and sub-group proportions are examined using the chi-square test; if the assumptions for the chi-square test are not satisfied, Fisher's exact test is used. Logistic regression compared outcomes for three groups: Control, AWEI Brochure and AWEI Research Educator. Future analyses will include logistic regression analysis to test hypotheses 3, 4, and 5. Odds ratios and their corresponding 95% confidence intervals are obtained. Statistical tests are two-sided, and a significance level of 0.05 is assumed for all tests.

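### Does the release rule that applies only to the Research Educator arm undermine the delivery-channel comparison in Hypothesis 2?

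*Combined protocol and SAP*

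**What the plan says.** Section 7.1 (Study assessments) makes three statements about timing.

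- Participants in every arm, control included, go to the recruiters "in a random fashion over the 15 days AWEI period starting at day 8". The stated purpose is to keep recruiters blind.
- For the RE arm, "survivors are released after the RE call is completed or the RE completed all 7 attempts to deliver the intervention".
- More generally, "we allow 15 days from the time from when the recruitment letter was sent to when the AMPLIFY recruitment call occurred".

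Section 5.1.2 supplies the calendar. RE phone attempts begin on day 5, with up to seven tries over ten days, so they end on about day 14 or 15. The brochure "was sent 4 days after the recruitment letter was sent" and has no completion condition. The same section says: "The same content was delivered in the AWEI-RE and AWEI-Brochure arms".

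Section 8.2 states: "Hypothesis 2 - Delivery channel: AWEI-Research Educator will have a significantly higher recruitment yield than AWEI-brochure". Section 8.3.2 tests this by randomised group within the AWEI participants, and section 8.3.1 says: "An intent-to-treat approach is used for statistical analyses". The primary endpoint in section 8.1 is consent among those screened and found eligible. Being reached by the recruiter is listed there as a post hoc outcome.

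**The concern.** Content is the same in the two channels, and Hypothesis 2 is labelled as a question about delivery channel, so channel appears to be the only difference under test. Release timing is a second difference. An RE survivor who answers early can be released early, and one who never answers is held until the attempts run out. Brochure survivors have no such dependence.

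Section 7.1 does not say whether the RE condition is added to the random release day or replaces it, nor how either relates to the 15-day allowance. No planned analysis describes release day or the interval from letter to call. If timing affected recruitment, a significant RE-versus-brochure result could be credited to the channel when some of it came from the calendar.

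**Working it through.** **The plan's own figure.** Hypothesis 2 is powered with 800 per group, 10% vs 20%, two-sided 5% (section 8.2). With the pooled-variance normal approximation:

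z = (0.10 × √800 − 1.96 × √(2 × 0.15 × 0.85)) / √(0.09 + 0.16) = (2.828 − 0.990) / 0.5 = 3.68, so power is 0.9999.

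This agrees with the stated figure of more than 95%. The release rule does not enter the calculation.

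**Assumptions for timing.** From the documents: random release from day 8 within a 15-day period; RE attempts from day 5 over ten days; brochure mailed on day 4. Assumed, because the documents are silent: random release day R is uniform on days 8–15 (mean 11.5); a share u = 0.1 to 0.7 of RE survivors is never contacted; the others are contacted on day C, either all on day 5 or evenly over days 5–14 (mean 9.5); attempts end on day 15.

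**Reading A: the RE condition is added to random release.** A contacted survivor is released on max(R, C). The mean is 11.5 if C = 5. If contacts are even, it is (4 × 11.5 + 11.625 + 11.875 + 12.25 + 12.75 + 13.375 + 14.125)/10 = 12.2. Those never contacted are released on day 15.

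- Lowest: 0.9 × 11.5 + 0.1 × 15 = 11.85, which is 0.35 days later than brochure.
- Highest: 0.3 × 12.2 + 0.7 × 15 = 14.16, which is 2.66 days later.

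**Reading B: it replaces random release, but nobody is released before day 8.** The contacted mean is 8 if C = 5, or (4 × 8 + 9 + 10 + 11 + 12 + 13 + 14)/10 = 10.1 if contacts are even.

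- Lowest: 0.9 × 8 + 0.1 × 15 = 8.70, which is 2.80 days earlier.
- Highest: 0.3 × 10.1 + 0.7 × 15 = 13.53, which is 2.03 days later.
- With u = 0.5 and C = 5: 0.5 × 8 + 0.5 × 15 = 11.50, no difference at all.

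If attempts end on day 14, the ranges become 0.26 to 2.05 days later (A) and 2.90 earlier to 1.33 later (B).

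**Second contact model.** A simulation with seven evenly spaced attempts and an assumed contact probability of 0.05 to 0.50 per attempt gave +0.1 to +2.0 days for A and −3.1 to +1.3 for B.

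**Other readings.** If survivors could be released before day 8, the RE mean would run from 0.9 × 5 + 0.1 × 15 = 6.0 to 0.3 × 9.5 + 0.7 × 15 = 13.35, but this goes against the day-8 start. If no call is made before day 15, the difference in call timing is about 0.

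**Would one common release day help?** Take release of everyone on day 15, and compare mean time from intervention to release for contacted RE survivors and for brochure survivors. The two values are for contacts even over days 5–14 and for contacts all on day 5.

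| Rule | RE call to release | Brochure mailing to release | Gap |
|---|---|---|---|
| Reading A | 12.2 − 9.5 = 2.7; 11.5 − 5 = 6.5 | 11.5 − 4 = 7.5 | 4.8; 1.0 |
| Reading B | 10.1 − 9.5 = 0.6; 8 − 5 = 3.0 | 7.5 | 6.9; 4.5 |
| All on day 15 | 15 − 9.5 = 5.5; 15 − 5 = 10 | 15 − 4 = 11 | 5.5; 1.0 |

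Under A the gap does not shrink; under B it shrinks but stays. Brochure and control survivors would also wait 15 − 11.5 = 3.5 days longer on average. Spreading release over days 15–22 would add 18.5 − 11.5 = 7 days on average and would overrun the 15-day participation stated in sections 1.1 and 4.3.

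**The case for a change.** The strongest case for a change is that release day depends on arm and reachability under every reading except the one with no call before day 15, and that even the sign of the mean shift turns on a rule section 7.1 leaves unstated. Hypothesis 2 is large enough for a modest artefact to matter. If timing alone moved yield by 1 or 2 points from 10% (assumed values, with all 800 per group counted), the test would reject with probability 10.5% or 28.7% without any channel effect. Stating the rule and tabulating intervals would cost little.

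The dependence on arm and the ambiguity both stand. The step to a defect in the analysis does not. The 1- and 2-point effects have no basis in the documents, and no mechanism is given by which a few days would alter consent among eligible survivors. Release is also not the call: the documents do not say how soon a call follows.

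Nor are the channels alike in everything except medium. They already differ in delivery day, in live contact and in the educator's offer to resend the letter (section 5.1.2). Section 2.2 poses a practical question, whether cheaper brochures can do the work of costly navigators, and a comparison of whole strategies answers it. Holding an RE survivor until the educator has finished keeps the recruiter from calling before the intervention is delivered. Hypothesis 1 compares any AWEI with none and makes no claim about channel.

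**Conclusion.** No change to the plan is needed. The asymmetry is real, but it is a fair trade-off in a phone-delivered intervention. Hypothesis 2 remains a valid intention-to-treat comparison of RE and brochure strategies, each with its own release timing. The mean shift is between about 3 days earlier and 3 days later, given uniform random release over days 8–15, the assumed contact rates and no release before day 8. Any effect on consent is unknown in size and direction. A common release day gives no clear gain, since it exchanges one timing difference for another at the price of longer waits.

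What remains is a gap in wording that does not alter the test. The manual of operations mentioned in section 9.1.4 may already settle how the release sentences combine, though it is not among the documents. The past tense in sections 5.1.2 and 8.3.1 suggests that delivery is over, so a new release rule may no longer be applicable. An analyst would ordinarily describe letter-to-release and letter-to-call intervals by arm and discuss Hypothesis 2 as a comparison of strategies. Release day would stay out of the main model, because it arises after randomisation and, in the RE arm, depends on reachability.

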7.2 ADVERSE EVENTS AND SERIOUS ADVERSE EVENTS

Risks and discomforts from participation in project activities for the AWEI trial are no greater than those associated with day-to-day living. No medical tests or procedures will be conducted, and no social, legal or other risks are anticipated.

Given this low risk there is no independent Data Safety and Monitoring Board (DSMB) for the AWEI trial, but will rely on the DSMB established for the AMPLIFI.

7.3 UNANTICIPATED PROBLEMS

7.3.1 DEFINITION OF UNANTICIPATED PROBLEMS (UP)

The Office for Human Research Protections (OHRP) considers unanticipated problems involving risks to subjects or others to include, in general, any incident, experience, or outcome that meets all of the following criteria:

- Unexpected in terms of nature, severity, or frequency given (a) the research procedures that are described in the protocol-related documents; and (b) the characteristics of the subject population being studied;
- Related or possibly related to participation in the research (“possibly related” means there is a reasonable possibility that the incident, experience, or outcome may have been caused by the procedures involved in the research); and,
- Suggests that the research places subjects or others at a greater risk of harm (including physical, psychological, economic, or social harm) than was previously known or recognized.

7.3.2 UNANTICIPATED PROBLEM REPORTING

To minimize the risk of **breach of confidentiality**, we will take the following precautions:

1. Investigators, recruiters, interviewers, the navigator and other study personnel, are, or will be, HIPAA and IRB certified prior to the handling of any personal data from study participants and must maintain current HIPAA and IRB certification as a requirement for continued employment.

2. Data on potential participants will be obtained from AMPLIFI. Identifiable data (name, addresses, phone numbers, emails) will be imported in Studytrax. Studytrax is an Electronic Data Capture system designed for clinical trials (Phase I – IV), observational studies and patient registries. Studytrax tracks subject enrollment and captures data elements via a secure web portal, and facilitates the transfer of data into statistical packages for analysis. Studytrax uses MS SQL Server as the back end relational database. In compliance with HIPAA privacy rules and HIPAA security rules, database security features target multiple levels including the data element (e.g., restricted access to fields), user (e.g., password authentication access), application (e.g., role-based access to features, access audit trails), and hosting services (e.g., firewall, secure sockets layer). Some of the most important features related to data security include: SSL enforced access, Strong authentication, All passwords are individually salted and hashed, Account locking after 5 failed attempts, Inactive user session time out, Role-based security, and User activity auditing. These features ensure access control, audit control, data integrity, user authentication, and transmission security.

The investigator will report unanticipated loss of confidentiality problems to the Institutional Review Board (IRB) of the University of Alabama at Birmingham (relying IRB) and the University of Tennessee Health Science Center. The report will include the following information:

- Protocol identifying information: protocol title and number, PI's name, and the IRB project number;
- A detailed description of the loss of confidentiality event;
- A description of any changes to the protocol or other corrective actions that have been taken or are proposed in response to the loss of confidentiality event.

To satisfy the requirement for prompt reporting, loss of confidentiality events will be reported within 10 working days of the investigator becoming aware of the problem.

8 STATISTICAL CONSIDERATIONS

8.1 STATISTICAL HYPOTHESES

- Primary Efficacy Endpoint(s):

Recruitment yield assessed by:

1) Consented if eligible: Binary indicator of whether the survivor who is screened and found eligible to participate in the AMPLIFY trial agrees and consents to participate in the AMPLIFY trial.

- Secondary Efficacy Endpoint(s):

Interest in participating in the AMPLIFY study and returned their consent assessed by:

Same as recruitment yield.

Post Hoc Outcomes:

- 1) Reached: Binary indicator of whether the AMPLIFY recruiter is able to reach the potential participant over the phone, regardless of whether the survivor is willing to receive information about AMPLIFY
- 2) Screened if reached: Binary indicator of whether the survivor who is reached by the recruiter is willing to consider the study and to be screened to ascertain eligibility for the AMPLIFY trial

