4.3 STRATEGIES FOR RECRUITMENT AND RETENTION

The AWEI trial was embedded into the AMPLIFI trial's recruitment process.² To identify the list of eligible survivors, AMPLIFI collaborated with the Alabama Statewide Cancer Registry (ASCR) and the North Carolina Registry (NCR), and followed their protocols for the release of contact information to the AMPLIFI research team. The AMPLIFI process started with survivors receiving a recruitment letter informing them about the study and of the possibility of receiving a call from an AMPLIFI recruiter. Survivors were also given the team's contact information to opt-out from the study if they so wished.

The AWEI trial randomization occurred once the recruitment letter was sent. No retention strategies were necessary since participation in the AWEI trial lasted 15 days. Outcomes were assessed as part of the AMPLIFY trial.

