8.3.2 ANALYSIS OF THE PRIMARY EFFICACY ENDPOINT(S)

Imbalances in randomization groups if any will be adjusted in analysis.

Outcome variables are categorical. We will use logistic regression to test for differences in outcomes across the randomized groups.

Hypothesis 1 will be tested using all randomized individuals. We will test differences in outcomes for 2 groups: AWEI (any combination) vs. no AWEI (control group).

Hypothesis 2 will be tested within the AWEI group. We will test differences in outcomes for 2 groups: AWEI-Research Educator vs. AWEI-brochure.

Exact 95% confidence intervals based on the binomial distribution will be determined for each proportion.

All statistical analyses will be conducted using SAS, version 9.4 (SAS Institute, Cary, NC).

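### As worded, the primary endpoint counts consent only among survivors screened and found eligible after randomization, so it can miss or reverse the recruitment gain the trial is meant to detect

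*Combined protocol and SAP*

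**What the plan says.** Section 8.1 equates recruitment yield with one indicator: "Consented if eligible: Binary indicator of whether the survivor who is screened and found eligible to participate in the AMPLIFY trial agrees and consents". The synopsis (1.1) gives the same definition. The secondary endpoint is declared identical to recruitment yield. The two earlier steps, reached and screened if reached, are listed in 8.1 as post hoc outcomes.

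Three other places point to a denominator of everyone randomized:

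- 8.3.1: "An intent-to-treat approach is used for statistical analyses".
- 8.3.2: "Hypothesis 1 will be tested using all randomized individuals".
- 8.2, where the power statement for Hypothesis 1 begins "With a minimum of 1,600 in the AWEI intervention group, and 400 in the no AWEI control group" and the section concludes "Thus, the trial is fully powered with a sample of 2,000 survivors". On a larger pool it says "If these are more than 2000, we will randomize all".

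On timing, 4.3 states: "The AWEI trial randomization occurred once the recruitment letter was sent". Under 5.1.2, brochures go out 4 days after the letter and research educator calls start at day 5. Under 7.1, survivors are released to the AMPLIFI recruiters from day 8. Those who are reached are offered screening, and further inclusion and exclusion criteria are checked only then.

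**The concern.** The objective is to find out whether AWEI increases recruitment to AMPLIFI. AWEI acts before the recruiter calls, so it can plausibly change who is reached and who agrees to be screened. In the educator arm, for example, the educator phones first, can explain why the call is being made and can resend the letter. Screening in turn determines who enters the denominator of the primary endpoint. Two consequences follow.

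- **Wrong question.** If AWEI brings more survivors into screening and they consent at the usual rate, recruitment rises but the primary test shows nothing. If the added survivors are less keen, the endpoint can fall while recruitment rises. If AWEI deters the less keen, the endpoint can rise with no gain in recruitment.
- **No randomized comparison.** The eligible subsets of the arms may differ in kind, and randomization does not protect a comparison between them.

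There is also a power question. Section 8.2 counts randomized survivors and does not say whether 10% and 20% are yields per randomized survivor or consent rates among eligibles. If they are the latter, the effective sample is smaller by an eligible share that the documents do not give.

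**Working it through.** **Inputs from the documents.** 400 control and 1,600 AWEI (H1); 800 per group (H2-H4); 200 per group (any two combinations); 10% vs 20%; two-sided chi-square test at 5% (8.2). **Assumed, because not in the documents:** the share f of randomized survivors who are screened and found eligible, and the counts in step 2.

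**1. Reproduce the stated power.** Power = Φ[(|p1 − p2| − 1.96·s0)/s1], with s0 = √[p̄(1 − p̄)(1/n1 + 1/n2)], s1 = √[p1(1 − p1)/n1 + p2(1 − p2)/n2] and p̄ the weighted mean rate.

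- H1, 400 vs 1,600: p̄ = 0.18, s0 = 0.02148, s1 = 0.01803; power 99.9% (stated > 95%).
- H2-H4, 800 vs 800: p̄ = 0.15, s0 = 0.01785, s1 = 0.01768; power 99.99% (stated > 95%).
- Any pair, 200 vs 200: p̄ = 0.15, s0 = 0.03571, s1 = 0.03536; power 80.2% (stated 80%).

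The figures are right on randomized counts. The > 95% for H1-H4 is also met on smaller counts, so it does not reveal which denominator was meant.

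**2. Can the endpoint and actual recruitment disagree?** Two-proportion z test with pooled variance, AWEI minus control, 400 and 1,600 randomized:

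| Assumed case | Consented / randomized | Consented / eligible |
|---|---|---|
| A. Eligible share 20% vs 40%, half consent in each arm | 40/400 vs 320/1,600 = 10% vs 20%; z = 4.66, p = 0.000003 | 40/80 vs 320/640 = 50% vs 50%; z = 0, p = 1.0 |
| B. Eligible share 20% vs 60%, 1/2 vs 1/3 consent | same, 10% vs 20% | 40/80 vs 320/960 = 50% vs 33%; z = −3.01, p = 0.003 |
| C. Eligible share 40% vs 20%, 25% vs 50% consent | 40/400 vs 160/1,600 = 10% vs 10%; z = 0 | 40/160 vs 160/320 = 25% vs 50%; z = 5.24, p < 0.001 |

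A misses a real gain, B reverses it, and C shows a gain where recruitment is unchanged. A milder form of B (eligible share 20% vs 50%; 40/80 vs 320/800, or 50% vs 40%) also points the wrong way, with p = 0.083.

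**3. Power if 10% vs 20% are rates among eligibles.** Replace each n by f·n, with f equal in all groups and 2,000 randomized:

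| f | H1 | H2-H4 | Any pair |
|---|---|---|---|
| 0.6 | 97.5% | 99% | 58% |
| 0.5 | 94% | 98% | 51% |
| 0.3 | 76% | 87% | 33% |
| 0.2 | 56% | 71% | 24% |

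95% power needs about 206 control plus 824 AWEI eligibles (H1) or 329 eligibles per group (H2-H4). 80% power for a pair needs 199 per group. The smallest f is then 206/400 = 0.515, 329/800 = 0.41 and 199/200 = 0.995. At an assumed 4,000 randomized, these halve to about 0.26, 0.21 and 0.50.

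**4. Does an all-randomized denominator secure the power by itself?** Not if 10% vs 20% are rates among eligibles. With f = 0.3 the yields per randomized survivor are 3% vs 6%, and power at 2,000 is 69%, 83% and 30%. With f = 0.5 (5% vs 10%) it is 92%, 97% and 48%.

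**The case against.** The best defence is that the sections can be read together. The hypotheses in 8.2 are about recruitment yield or efficacy in general, 8.2 attaches 10% vs 20% directly to randomized group sizes, and 8.3.1 and 8.3.2 speak of intent-to-treat and all randomized individuals. If every survivor who did not consent counts as no, everything agrees and the stated power stands. That coding rule is written nowhere, however, and the words *if eligible*, alongside the parallel *screened if reached*, point the other way. Two analysts could follow this plan with different denominators.

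Second, the all-randomized phrase in 8.3.2 is set against Hypothesis 2 being tested within the AWEI group, so it may only say which arms enter the test. That softens the contradiction with 8.3.2. It does not help the endpoint, because 8.3.2 then supplies no all-randomized denominator.

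Third, cases B and C are extreme: AWEI triples the eligible share in one and halves it in the other. Some criteria checked at screening, such as completed primary treatment, are unlikely to respond to a brochure or a call. This is fair, and the cases show what is possible, not how likely it is. Case A needs only more survivors entering screening and an unchanged consent rate.

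Fourth, the synopsis lists all three steps as endpoints, so part of an effect would be visible. But 8.1 makes the first two post hoc, and screened if reached is itself conditional. Neither replaces consent per randomized survivor.

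Fifth, the loss of power is conditional. H1-H4 keep their > 95% if f is high enough, and randomizing more than 2,000 lowers the thresholds. This stands, so power is the secondary point.

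**Conclusion.** The concern holds. As worded, the sole primary endpoint is defined on a subset formed after randomization and open to influence by the intervention. No section says how survivors who are not reached, not screened or not eligible are coded. The choice of denominator can change the trial's conclusion: in case A it alone moves the result from p = 0.000003 to p = 1.0. That example rests on assumed rates; the conflict in the text does not.

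The stated power is arithmetically correct for 10% vs 20% of randomized survivors. If those are rates among eligibles, the effect depends on an unstated f. At 2,000 randomized, H1 falls below 95% once f is under about 0.515 and H2-H4 once f is under about 0.41. The pairwise 80% has practically no reserve at 200 per group. This must be fixed before the primary result is interpreted.

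**What to change.** - **8.1 and synopsis:** define the primary endpoint as consented to AMPLIFI, yes or no, among all survivors randomized. Code those who opted out, were not reached, were not screened or were ineligible as no. Use it for H1-H5.
- **Funnel steps:** report reached, screened and consented as counts over all randomized. Keep screened if reached and consented if eligible as descriptive rates without causal claims.
- **8.2:** state that 10% vs 20% are yields per randomized survivor and give their basis. If they are rates among eligibles, or if the conditional endpoint is kept, restate the power using the expected eligible share.
- **Timing:** 8.3.1 is partly in the past tense ("Logistic regression compared outcomes for three groups"), so results may already be known. If outcome data have been seen, date the change, label it post hoc and report the all-randomized analysis beside the endpoint now in 8.1.

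The cost is an amendment covering the endpoint wording, the coding rule and 8.2. No new data are needed, because the recruiters already track these outcomes (7.1). The change of denominator does not by itself guarantee the stated power, so the 8.2 clarification is needed as well.
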